#### **Follow up tests and procedures:**

After the completion of the 6 month exercise intervention, all men will be followed for an additional 6 months after formal training stops. Men will continue to track their falls during the follow-up period using the same monthly reports employed in the intervention phase. We recognize that men may wish to maintain their exercise habits after formal training stops and we will not discourage them from doing so. During the follow-up period, exercise questionnaires will be used to track participation in home or community exercise programs and will be collected at the 9- and 12-month time periods.

The total duration of an individual subject's participation in the study is 12 months. Certain data (questionnaires, adverse events follow-up, and Release of Information forms) may be collected after this 12-month period, when a participant is off study, using IRB-approved language.

When participants drop out of the research their data will be retained for analysis. If a participant becomes ineligible during the study he will be withdrawn by the investigator and data will no longer be collected; however, in these cases the participant would be allowed to continue in the study exercise program as long as the reason for ineligibility does not contraindicate exercise participation.

The investigator may choose to withdraw a participant without their consent if his health changes and the study is no longer in their best interest, if new information becomes available, if he does not follow the study rules, and/or if the study is stopped by the IRB.

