## 13.0 BIO-STATISTICAL CONSIDERATIONS

### Power and Sample Size

We have powered the sample size based on our primary aim. In older adults, 20%-30% of community-dwelling elders are likely to fall within 1 year [11] and Li and others have reported a reduction in fall risk of 47% from 3 [86] or 6 [41] months of tai ji quan exercise. We are using an effect size for tai ji quan to power for both interventions because we have these data available from our prior work and effects sizes for strength training are similar to tai ji quan [87]. Our study will determine if strength training is as effective as tai ji quan. Using PASS 2008[88], based on a negative binomial regression model [89], at alpha = .05, the variance shared among the dummy vectors representing treatment ( $R^2=.25$ ), and an estimate of the overdispersion parameter (Phi) of 2.5, a sample size of n=300 (n=100 per group) participants will provide 80% power to detect at least a 47% reduction in the fall incidence rate over six months by being in either of the 2 exercise groups versus control. To protect against an estimated attrition of ~17% during the intervention period, 120 participants will be randomized per group (total sample size: N=360). The attrition estimate is conservatively based on the highest attrition rate from our prior strength training trials in prostate cancer survivors (0% and 16% attrition in 6 and 12 month trials, respectively [37, 39]). Though the total # of falls is the primary endpoint, the sample size of N=300 also provides sufficient power to detect differences between experimental and control groups on secondary outcomes of frailty and physical function. We and others' have data on the effect of exercise on individual components of frailty in prostate cancer survivors on ADT and self-report physical function. With a sample of N=100 per group we have a sufficient sample to detect a difference in 2.5% of lean body mass [90, 91], a 4 sec. faster chair stand time [37, 91], a 1.1 sec. faster gait speed [91], and a 9% difference in self-report physical function scores [37].

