All analyses will retain each participant in the group he was randomly assigned regardless of missing data or drop out status (i.e., intention to treat). We will track medical treatment changes and disease progression during the study to describe the sample or justify why participants exited the study. In the unlikely event of a large subgroup, these data could be used for exploratory subgroup analysis to suggest directions for future research. Age, timing of ADT (current vs. past), fall history at enrollment and baseline frailty will be considered as possible covariates in all analyses. Age and timing of ADT (past vs current) are included since they may affect exercise tolerance and/or responsiveness to exercise training; fall history is included because we want to examine the efficacy of the interventions to reduce falls in men with a fall history and prevent falls

among men who have not recently fallen. Analyses will be conducted in Stata, R, and/or Mplus statistical software packages. Full information maximum likelihood estimation (FIMLE) will be used to estimate the models, as appropriate, because it is less biased and more efficient than other techniques for handling missing or incomplete data[92].

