Aim 1: Compare the relative efficacy of tai ji quan and strength training to prevent falls: We will determine the efficacy of tai ji quan and strength training by comparing each of them to the control condition while adjusting for important covariates using negative binomial regression models which will analyze total number of falls per participant that occur from baseline to 6 months. A negative binomial regression was chosen over a Poisson regression for modeling the count data because of the overdispersion that is common with actual research data. [88, 93] Intervention type will be entered into the model as 2 dummy variables, with the reference group being the control group. This will allow a comparison of the each of the intervention groups against control. A *second* model will be run with strength training as the reference category to compare the intervention groups to each other. In addition to standard ITT analysis, the impact of participants who drop out of the study on the falls outcome will be examined in a secondary data analysis. A significant incidence rate ratio (IRR) less than 1.0 for the dummy vector representing tai ji quan and/or strength training would provide support for the hypothesis that the respective intervention reduced the rate of falls compared to the control group.

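### The Aim 1 falls model yields a rate ratio but states no exposure term, and Section 8.0 separately ends data collection on men who become ineligible (low to moderate severity)

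*Combined protocol and SAP*

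**What the plan says.** Section 13.0, Aim 1, specifies "negative binomial regression models which will analyze total number of falls per participant that occur from baseline to 6 months". The terms named are two treatment indicators and covariates. Support for the hypothesis is read from "A significant incidence rate ratio (IRR) less than 1.0 for the dummy vector representing tai ji quan and/or strength training". The power paragraph also speaks of a rate: the sample is sized "to detect at least a 47% reduction in the fall incidence rate over six months". No section mentions an offset, person-time or months observed for falls.

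Four statements bear on incomplete follow-up:

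- Randomised numbers are raised "To protect against an estimated attrition of ~17% during the intervention period".
- On the analysis set: "All analyses will retain each participant in the group he was randomly assigned regardless of missing data or drop out status". The same part of Section 13.0 names full information maximum likelihood, where suitable, for incomplete data.
- Section 8.0: "When participants drop out of the research their data will be retained for analysis".
- Aim 1 adds that "the impact of participants who drop out of the study on the falls outcome will be examined in a secondary data analysis", without giving a method.

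Section 8.0 also has a separate rule for a man who becomes ineligible after enrolment. He is withdrawn and collection of his data ends, but he may go on exercising with the group if the reason does not rule exercise out. Falls are otherwise reported every month to month 12 (Section 3.0 and the Schedule of Events).

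**The concern.** A total that covers three months is not comparable with one that covers six. Because partial records are kept and everyone is analysed, the primary model must say how a short record enters it. The text allows at least three readings: the short count stands as a six-month total; it is modelled as a rate with an offset; or the man's total is treated as missing. Two analysts could follow the plan faithfully and report different primary IRRs. Aim 3 inherits the gap, because it reuses the same falls model in two periods split at month 6.

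The ineligibility rule is a different kind of problem. It discards primary-outcome data that the monthly system could still collect. Section 8.0 does not say which criteria apply after enrolment. Those listed in Section 5.0 include prostate cancer therapy other than ADT and medical conditions or medication that rule out moderate exercise. Section 8.0 also lets the investigator withdraw a man whose health changes. Such reasons can be related to fall risk, so the loss may be informative, and no offset repairs it.

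**Working it through.** **The plan's own figure.** Inflating for 17% attrition gives 100/0.83 = 120.5 (121) per group and 300/0.83 = 361.4 (362) in total, against the stated 120 and 360. Going from 120 to 100 is 16.7%, so the figure reproduces to rounding. The 80% power claim cannot be checked, because the control fall rate is not stated.

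**Shift from raw totals.** With a log link and arm indicators, the fitted ratio is the ratio of arm means. If a share d of an arm drops out and dropouts are observed for a mean share f of the six months, mean follow-up is 1 − d(1 − f), so

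factor = [1 − d_ex(1 − f)] / [1 − d_ctl(1 − f)].

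The 0.53 is the planned 47% reduction. The attrition splits and f are assumptions.

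| Control / exercise | f | Factor | 0.53 becomes |
|---|---|---|---|
| 17% / 17% | 1/2 | 0.915/0.915 = 1.000 | 0.530 |
| 16% / 18% | 1/2 | 0.910/0.920 = 0.989 | 0.524 |
| 14% / 20% | 1/2 | 0.900/0.930 = 0.968 | 0.513 |
| 20% / 14% | 1/2 | 0.930/0.900 = 1.033 | 0.548 |
| 14% / 20% | 1/3 to 2/3 | 0.956 to 0.979 | 0.507 to 0.519 |
| 20% / 14% | 1/3 to 2/3 | 1.046 to 1.021 | 0.555 to 0.541 |

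**Against sampling error.** Assume 120 per arm, mean observed share 0.915, control mean 0.3 to 1.0 falls per six months, and per-arm variance of either (1/m + k)/120 with k = 1.0 or 2.5, or 2.5/(120m), where m is the arm's mean observed count.

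- Smallest SE at IRR 0.53 (control mean 1.0, k = 1.0): √[(1/0.915 + 1 + 1/0.485 + 1)/120] = 0.207.
- Largest SE at IRR 0.53 (control mean 0.3, inflation 2.5): √[2.5(1/0.2745 + 1/0.1455)/120] = 0.468.
- At IRR 1.00 the range is 0.187 to 0.390.

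For 14%/20% or its reverse, |log factor| = 0.033. That is 0.033/0.468 = 0.07 to 0.033/0.187 = 0.18 SE. Type I error becomes 5.08% to 5.35% instead of 5.0%. Power at 0.53 moves by about 2 to 5 percentage points either way.

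**Simulation check.** Negative binomial fits with true IRR 0.53, 5,000 per arm, 80 replicates, k = 1.0 or 2.5 and dropout times uniform over 0.1 to 1.0 of the period gave:

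- 14%/20%: raw 0.512–0.516, offset 0.527–0.530.
- 20%/14%: raw 0.543–0.549, offset 0.527–0.533.
- 17%/17%: raw 0.529–0.535, offset 0.529–0.534.

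**Where the offset does not help.** Suppose the effect is absent until month 3 and 0.53 afterwards (assumed). The true six-month IRR is (3 + 3 × 0.53)/6 = 0.765. With dropout uniform over six months, a dropout contributes on average 2.25 months before month 3 and 0.75 after.

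- 14%/20%: exercise falls, in units of the control monthly rate, are 0.80 × 4.59 + 0.20 × 2.6475 = 4.2015. Raw: 4.2015/5.58 = 0.753. Rate: 4.2015/5.40 = 0.778. The offset is marginally further from 0.765.
- 20%/14%: exercise falls are 0.86 × 4.59 + 0.14 × 2.6475 = 4.318. Raw: 4.318/5.40 = 0.800. Rate: 4.318/5.58 = 0.774. The offset is clearly closer.

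**Ineligible men.** No rate of post-enrolment ineligibility is given, so no size is calculated.

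**The case against.** The strongest reply is that this is a wording gap. The power paragraph and Aim 1 both speak of a rate, and monthly reports supply the denominator, so a competent analyst would probably use an offset. The 17% is a deliberately cautious margin: Section 13.0 takes it from the highest attrition in the team's earlier strength trials, 16% over 12 months, against 0% in a six-month trial. Section 3.0 reports that an earlier stretching control retained men about as well as strength training, and that two prior studies obtained 98% of monthly fall reports over six months. All of this stands and keeps the point small. It does not state the exposure term, and no retention figure is given for tai ji quan in this population.

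The missing-data sentence and the secondary dropout analysis might also be cited. Neither says how a partly observed count enters the primary model.

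On ineligibility, most inclusion criteria are historical and cannot be lost, and a man whose condition rules out exercise is not among those who stay in class. The plan also says: "We will track medical treatment changes and disease progression during the study to describe the sample or justify why participants exited the study". That suggests a treatment change need not end data collection. These points limit how many men may be affected, but the rule as written still stops data collection for any man judged ineligible.

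A reader might infer a large bias from the 25% versus 0% attrition in Section 3.0. The documents do not support that: the gap arose with a usual-care control and is given as a reason for choosing stretching instead.

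**Conclusion.** The point holds at low to moderate severity. The primary model is under-specified. Read literally, it biases the IRR only when follow-up differs between arms: not at all at equal attrition, and from 0.53 to about 0.51 or 0.55 at an assumed six-point gap, which is at most 0.18 SE. The case rests on removing an ambiguity in the primary analysis at almost no cost, not on a large expected error.

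The ineligibility rule is an avoidable and possibly informative loss of the primary outcome. Its size is unknown and it carries no numerical weight here. A reader might call it a contradiction of the intention-to-treat statement. That goes too far: a man can be kept in his assigned group with the data he has. The two statements sit poorly together and should be reconciled.

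Nor does the text show that the sponsor intends raw totals. It permits them and does not require an offset.

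**What to change.** 1. **Model.** In Aim 1, and in each period of the Aim 3 falls model, include log(months with an observed fall report) as an offset, counting falls and months from the same reports. A man with no reports in a period has no defined offset. Report by arm the men with no post-baseline fall data, cover them in the dropout analysis already planned, and state how that relates to the full information maximum likelihood sentence.
2. **Data collection.** In Section 8.0, continue the existing monthly fall report to month 12 for men who become ineligible or stop the programme, and analyse them as randomised. Exceptions are withdrawal of consent, an IRB stop, or the investigator's judgement that continued contact is not in the man's best interest. If follow-up is already complete, which the documents do not say, report these men by arm and reason. This concerns data collection only, not who may keep exercising.

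**Cost.** A line in each falls model, a sentence in Section 8.0, a few more reports of one to two minutes each, and a small amount of extra analysis.

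**Limits.** The offset corrects unequal observation time only. It does not correct dropout related to fall risk or an effect that changes over time, and in the step-effect example at 14%/20% it is marginally further from the truth than raw totals.

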Aim 2: To determine and compare the efficacy of tai ji quan training and strength training to reduce frailty and dysfunction: Each participant will be classified as frail, pre-frail or robust based on his total frailty score (see **Measures**). We hypothesize that the number of men classified as frail or pre-frail will decrease over the course of the study in the tai ji quan and strength training groups compared to control. Formal tests of frailty hypotheses will be conducted in a generalized mixed effects modeling framework as implemented in the R statistical computing environment. [94] Frailty category will be the multinomial dependent variable (with “robust” as the reference group) and study time point (0, 3 and 6 mos.), group (control as the reference group) and the group x time interactions will serve as predictors. [95] We will also run a second model with strength training as the group reference category to compare the two experimental groups to each other. Significant group x time interactions will indicate that the distribution of frailty between the groups (e.g., tai ji quan vs. control) is different across time. For significant interactions, additional contrasts testing for frailty differences will be examined to describe the pattern of change across time. Group differences across time in the continuous physical function and individual frailty measures will be tested in a linear mixed effects modeling framework [94] to estimate the trajectory of change in each dependent variable across time for each individual in each group, and then comparing the average trajectories across groups. The primary effect of interest is a cross-level interaction. Specific hypotheses about treatment group effects will be specified by adding dummy variables and hypotheses will be tested through group x time interactions (as above). We will also evaluate the practical significance of the interventions by summarizing results with respect to effect size.

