Aim 3: Determine how well the benefits of each intervention persist after structured training stops: We will use the same modeling strategies described above for each outcome (i.e., negative binomial regression, multinomial/linear mixed effects models). However, we will perform the analyses piecewise, with a change point occurring at 6 months. Of particular interest is whether the observed effects for the treatment groups differ or remain the same after the change point. In addition, we will examine whether participation in exercise following the end of the intervention moderates the persistent effect of the intervention on study endpoints. We will categorize the type of exercise participants engaged in (i.e., walking/aerobic, strength training, tai ji quan, stretching) for at least 50% of the follow-up period. These categories will then be dummy coded and entered into the analyses outlined above, along with the product of these dummy vectors and treatment to represent the interaction. A significant coefficient for the product term would indicate that continued exercise modifies the effect of the intervention on falls, frailty, or physical function. This

analysis will allow us to determine whether continued participation in an exercise program maintained improvements for an intervention group or a lack of participation caused a loss of improvements in an intervention group, and whether control participants who begin programs similar to the intervention programs improve in outcomes.

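### Aim 3 tests moderation by follow-up exercise with a term that has no time index; fitted in one model over months 0–12, it pools outcomes from before that exercise took place

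*Combined protocol and SAP*

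**What the plan says.** The Aim 3 paragraph of section 13.0 carries over the models of Aims 1 and 2, with one change: "we will perform the analyses piecewise, with a change point occurring at 6 months". It then states the moderation question: "we will examine whether participation in exercise following the end of the intervention moderates the persistent effect of the intervention on study endpoints". The moderator is the type of exercise a man did "for at least 50% of the follow-up period". According to section 8.0 (Follow up tests and procedures), the exercise questionnaires behind it "will be collected at the 9- and 12-month time periods".

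The exercise categories are dummy coded and "entered into the analyses outlined above, along with the product of these dummy vectors and treatment to represent the interaction". The plan also fixes how the result is read: "A significant coefficient for the product term would indicate that continued exercise modifies the effect of the intervention on falls, frailty, or physical function".

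Two other places bear on this. Section 3.0 (Measures and Data Collection) places the frailty and function assessments at enrollment, 3, 6 and 12 months. The Aim 2 paragraph of section 13.0 tests treatment hypotheses through interactions of group with time; the Aim 3 moderator sentence does not repeat that device.

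**The concern.** Exercise in months 7–12 cannot affect a man's baseline, month-3 or month-6 value, or his falls in months 0–6. A product of exercise type and treatment with no time factor takes a single value across everything in the model. If the model holds data from both sides of month 6, that value is an average of the exerciser versus non-exerciser difference in the arm contrast, taken mostly (visits) or partly (falls) over time before the exercise.

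Two errors follow. A real modification after month 6 is diluted. And because continuing is each man's own choice, a difference that already existed by month 6 can make the term significant, and the plan would read this as continued exercise modifying the effect. Aim 3 relies on this analysis to say whether continued participation maintained the improvements.

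**Working it through.** The plan gives no power or effect size for this test, so there is no stated figure to reproduce.

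**Inputs from the plan.** Visits at 0, 3, 6 and 12 months; 100 men per group; alpha 0.05 (sidedness not stated; two-sided used here); a 47% reduction in falls, so a rate ratio of 0.53; overdispersion 2.5.

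**Assumed inputs.** One exercise arm against control, one exercise type, half of each arm continuing (50 men per cell), outcome SD 1, and equal correlation between visits.

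**1. Continuous measures: dilution.** With complete data and arm-by-visit terms, the time-constant product estimates the four-visit average.
- A modification of 0.40 SD at month 12 only becomes 0.40/4 = 0.10.
- With visit correlation 0.7, the variance of the four-visit mean is (1 + 3×0.7)/4 = 0.775. SE = √(0.775×4/50) = 0.249, z = 0.10/0.249 = 0.40, power about 7%.
- Month 12 alone, adjusted for baseline and month 6: R² = 2×0.7²/(1 + 0.7) = 0.576, residual variance 0.424. SE = √(0.424×4/50) = 0.184, z = 0.40/0.184 = 2.17, power about 58%.

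Simulation gives 7% against 57–59%. At 0.6 SD it gives 10% against 89%. With correlation 0.6 and a gain of 0.50 SD kept only by exercisers, the estimate is 0.12 and power 7%, against 53% for a term tied to the post-6-month segment.

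**2. Continuous measures: false signals, with no modification after month 6.**
- A 0.4 SD difference present from baseline, correlation 0.6: SE = √(0.70×4/50) = 0.237, z = 0.40/0.237 = 1.69, so about 39% rejections. Simulation gives 39%, against 4% for the post-6-month term.
- A 0.4 SD difference arising during the intervention: 19% against 6%.
- Strength-arm men continuing according to month-6 fitness (logit slopes 0.3, 0.5 and 1.0 per SD): 15%, 33% and 74%, against 4–5% for the adjusted month-12 model.

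**3. Falls, two six-month periods.** With equal numbers, the two-way product recovers the ratio of summed rates within the exercise arm (control rate set to 1).
- True maintenance: continuers 0.53 then 0.53, others 0.53 then 1.00. The product gives (0.53 + 0.53)/(0.53 + 1.00) = 0.69; the follow-up truth is 0.53. On the log scale, 0.367/0.635 = 58% of the effect remains.
- Power with 0.75 control falls per six months and heterogeneity variance 1: 17% as written, 29% for the follow-up contrast.
- Power with 1.13 control falls and dispersion 1.33: 16% against 37% for a modifying ratio of 0.53, and 24% against 64% for 0.40. The plan states no base rate. The value 1.13 is what its 80% power would need (two-sided, one third exposed), and 1.33 = (2.5 − 1)/1.13.
- Difference before month 6 only: continuers 0.35 then 0.53, others 0.71 then 0.53. The product gives (0.35 + 0.53)/(0.71 + 0.53) = 0.71, flagged 15% of the time against 6%.
- If 60–70% of exercise-arm men without falls continue, and 30–40% of those with falls: 16–49% false positives, against 5–7% for the adjusted follow-up model.

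**4. Would a three-way product cure it?** Exercise × arm × period, with its lower-order terms, is a change contrast.
- For falls in the last case but one it gives (0.53/0.53)/(0.35/0.71) = 2.03, although nothing differs in follow-up. When men continue according to earlier falls, it rejects 11–28% of the time, with ratios of 1.3–1.9.
- For continuous measures under the selection in step 2, it rejects 6–7% when month 12 is set against the mean of the three earlier visits, but 7%, 11% and 20% when set against month 6 alone.

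**The case against.** The best defence is that the sentence is loose rather than wrong. Aim 1 models one total count per man, and no repeated-count model is described anywhere, so running it piecewise could mean one count model per segment. In a months 7–12 model, exercise by treatment is the right term for falls. For frailty and function, the Aim 2 framework models individual trajectories and its main effect of interest is a cross-level interaction. A person-level product could enter there as a predictor of the post-6-month slope, and would then carry time implicitly. The stated target, the persistent effect, points the same way.

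This stands as far as it goes: the text permits those readings. But it states none of them. It names the two factors in the product and the coefficient to be read, and an analyst who follows it literally in a single change-point model fits the pooled term.

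Two further points also stand. The adjusted model does well in the selection scenarios partly because it conditions on the variables that drove selection there. And the correlations, fall rates and continuation rates are not in the documents; the 74% figure needs strong selection in one arm only.

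A reader might infer that the Aim 3 moderation result is certain to be invalid, or that the falls analysis would miss maintenance altogether. The documents do not support either: separate segment fits are possible, and for falls the loss is dilution.

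**Conclusion.** The point holds in conditional form. The plan gives the moderator product no follow-up index. If one model spans months 0–12, a modification at month 12 only shrinks to a quarter for visit-based measures (power about 7% where a follow-up-only test has about 58%, at 0.40 SD and correlation 0.7). For falls, 0.53 is estimated as 0.69. Differences from before month 6 can be reported as an effect of later exercise. If segments are fitted separately, the product is adequate for falls.

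The direction follows from where the term sits; the sizes depend on the assumptions listed. The matter is confined to a moderation analysis within a tertiary aim and does not touch the Aim 1 or Aim 2 tests. It is worth correcting because the plan commits to a specific reading of this coefficient.

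**What to change.** In the Aim 3 paragraph of section 13.0, confine the moderator test to follow-up:
- **Falls:** model the count in months 7–12 on arm, exercise type and arm × exercise type, adjusting for the man's own falls in months 0–6.
- **Frailty and function:** model the 12-month value on the same terms, adjusting for his baseline and 6-month values.
- **If one piecewise model is kept for continuous measures:** name exercise type × arm × post-6-month segment, with all lower-order terms, as the tested coefficient, and state which earlier visits it is set against. A contrast with month 6 alone is the more exposed to selection.
- **Do not use that three-way change contrast for falls**, because it gives false positives when men continue exercise according to their earlier falls.

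The cost is SAP wording; data and software are unchanged. There are downsides to state alongside it. Adjusting for month-6 status makes this a test of change since month 6, and that status is itself affected by treatment. The comparison remains observational. Power for falls stays low (29% to 37% for a modifying ratio of 0.53 under the inputs above).

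### Aim 3 judges whether continued exercise modifies the effect by a single product-term coefficient, but the model described has eight such terms (16 for frailty) and no joint test

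*Combined protocol and SAP*

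**What the plan says.** Section 13.0, Aim 3, adds a moderation analysis to the persistence analysis. Exercise taken up after the supervised programme is grouped by type: "We will categorize the type of exercise participants engaged in (i.e., walking/aerobic, strength training, tai ji quan, stretching"), counted if kept up for at least half of follow-up. Then: "These categories will then be dummy coded and entered into the analyses outlined above, along with the product of these dummy vectors and treatment". The interpretation rule is: "A significant coefficient for the product term would indicate that continued exercise modifies the effect of the intervention on falls, frailty, or physical function". The paragraph ends by saying that the analysis will settle whether continuing to exercise kept the gains, whether stopping lost them, and whether controls who start similar programmes improve.

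Other paragraphs of section 13.0 supply the structure:
- Aim 1 on treatment: "Intervention type will be entered into the model as 2 dummy variables, with the reference group being the control group".
- Aim 3 on the models: "We will use the same modeling strategies described above for each outcome", fitted piecewise with a change point at 6 months.
- Aim 2 on frailty: "Frailty category will be the multinomial dependent variable", with three categories.
- The sample-size paragraph contains the only significance level for the main trial ("at alpha = .05, the variance shared among the dummy vectors representing treatment").

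Aim 3 names no level, no joint test, no multiplicity adjustment, no reference category for exercise type, and does not say whether a man can belong to more than one type.

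**The concern.** The rule speaks of one product term, but the model described contains several. If each is tested at the usual level and a significant one is taken as a sign of modification, the chance of a false sign is well above 5%. This would hold even if follow-up exercise had been assigned at random, so it is separate from the problem that men choose their own exercise.

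At stake is the advice drawn from Aim 3: whether men need to keep exercising after a supervised programme, and in which form, to hold the benefit. A chance finding for one exercise type in one arm could be reported as the answer.

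**Working it through.** The documents give no error rate for this analysis, so there is no plan figure to reproduce. The quantity needed is the probability that at least one treatment-by-exercise product is significant when there is no modification.

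**Inputs from section 13.0:** 2 treatment dummies; 4 exercise types; 3 frailty categories, hence 2 logits; 300 evaluable men, 100 per arm (360 randomized, 120 per arm); overdispersion 2.5.

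**Assumptions not in the documents:** .05 two-sided per coefficient, carried over from the sample-size paragraph; the share of men in each exercise type; a mean of 1.1 falls per man. With negative binomial dispersion 1.4, that mean gives variance/mean = 1 + 1.4 × 1.1 = 2.54, close to the plan's 2.5.

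**Step 1: count the terms.**
- Non-exercisers as reference, or overlapping types: 4 × 2 = 8.
- One named type as reference: 3 × 2 = 6.
- Frailty with the first coding: 2 logits × 8 = 16.

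**Step 2: benchmark if the tests were independent,** 1 − 0.95^k.
- k = 6: 26.5%
- k = 8: 33.7%
- k = 16: 56.0%

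**Step 3: allow for correlation.** The products share the control arm, so their estimates are correlated and the rate falls. Using the covariance of the product-term coefficients with 100 men per arm, and 400,000 multivariate normal draws:

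| Coding | Terms | At least one p < .05 |
|---|---|---|
| Overlapping types, each 20–50% of men | 8 | 31.1–31.5% |
| Exclusive types, 60% non-exercisers | 8 | 31.2% |
| Exclusive, 40% non-exercisers | 8 | 30.1% |
| Exclusive, mix of types differs by arm | 8 | 30.3% |
| Exclusive, 20% non-exercisers | 8 | 26.9% |
| Exclusive, 12% non-exercisers | 8 | 23.8% |
| Exclusive, 4% non-exercisers | 8 | 18.2% |
| One named type as reference, equal groups | 6 | 22.0% |

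**Step 4: direct simulation with no modification.**
- Linear model, eight terms, 300 or 360 men, 4,000 runs per setting: 26.1–33.2%.
- Negative binomial falls, eight terms, 300 men: 25.5–27.7% (1,500 runs per setting). A second set of 600 runs per setting gave 27–34%, with a Monte Carlo standard error of about 2 points.
- Multinomial frailty at one time point, 16 terms, 600 runs per setting: 34.7–47.5%. With exclusive types only 476 of the 600 fits converged.

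**Step 5: the alternatives.**
- One joint 8-df test of all products: 4.3–5.6%. A separate falls simulation with the dispersion treated as known gave 6.1–6.3%.
- Bonferroni at .05/8 = .00625 per term: 2.9–4.7% across the codings in the table.

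**Limits.** The simulations are cross-sectional. The planned piecewise mixed models could add products with time, and a second model with strength training as reference would add further contrasts; both would raise the count. The joint test was not simulated for frailty.

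**The case against.** The strongest reply is that the singular is loose drafting. The closing sentence of Aim 3 poses several distinct questions, and for distinct questions an error rate per contrast is a recognised choice. That would stand if the plan tied each term to its own question. Instead the rule draws a general conclusion, that continued exercise modifies the effect, and the paragraph claims to settle the matter.

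A second reply is that this is an add-on within a tertiary aim, so it can be taken as exploratory. It is indeed an add-on: the tertiary hypothesis in section 2.0 concerns persisting group differences and says nothing about moderation. But the plan has a separately named Exploratory Aim, and this analysis is not in it. If the sponsor regards it as exploratory, one sentence would say so.

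A third reply is that the rate depends on unstated choices. That stands, and it is why a range is given. Every coding tried is nevertheless well above 5%; the lowest value, 18.2%, requires that only 4% of men do no exercise.

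Two stronger readings should be resisted. A reader might infer that the plan accepts any one significant term as proof. The text says only that a significant coefficient would indicate modification, and it simply gives no other rule for several terms. A reader might also multiply the rate across outcomes and conclude that a false modifier somewhere is likely. The documents do not support a figure for that: the number of outcomes tested is not fixed, and all are measured in the same men, some of them being components of frailty, so the errors are unlikely to be independent.

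**Conclusion.** The point holds. As written, the Aim 3 rule does not fit the model it is attached to. With no true modification, at least one product term would be significant in about 27–33% of analyses of falls or of a continuous outcome under ordinary eight-term codings, and in about 18–34% over all six- and eight-term codings examined. For frailty, with 16 terms, the figure is about 35–48%, from a simplified simulation in which some fits failed. These figures rest on .05 per coefficient and on assumed exercise prevalences, neither of which Aim 3 states. A joint test brings the eight-term rate close to 5%.

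This should be corrected, but its reach is limited. The primary falls comparison at 6 months is not affected, nor is the comparison of randomized groups during follow-up when fitted without these terms.

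**What to change.** In the Aim 3 paragraph of section 13.0:
1. State the reference category for follow-up exercise, whether types may overlap, and whether the products also involve time.
2. Replace the single-coefficient rule with one joint likelihood-ratio or Wald test per outcome of all treatment-by-exercise-type products. Its degrees of freedom should match the fitted model: 8 for falls and continuous outcomes and 16 for frailty under the coding above. Interpret individual terms only if the joint test is significant.
3. Label the moderation analysis exploratory, because one test per outcome does not control error across outcomes.
4. Say what will be done if the 16-term frailty model does not converge, for example combining exercise types.

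The cost is a few sentences and one model comparison per outcome, with no new data. A joint likelihood-ratio test also gives the same answer whichever arm is the reference, so the second reference-group model needs no further test of its own. The price is somewhat less power to declare a modifier confined to one exercise type in one arm.
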